***Nasal lavage procedure:***

Both nares will be lavaged. A standard amount of saline will be sprayed into each nare using a nasal meter dosed sprayer which delivers 100ul/actuation. Each lavage is comprised of eight sets of five sprays. Lavage fluid will be recovered by forceful expulsion of lavage fluid into a specimen cup immediately after each set of 5 actuations. Samples will then be transported on ice to the laboratory where slides for differential cell counts of uncentrifuged NLF will be made. The remainder of each specimen will be centrifuged and stored at -70° C until further analysis.

***Nasal epithelial lining fluid (ELF) collection procedure:***

ELF is obtained by spraying the nostril with 0.9% sterile, normal saline irrigation solution (about 100 µl per nostril) one time per nostril. One 10x55mm strip of filter paper, cut from Leukosorb paper (Pall Scientific, Port Washington, NY) on a laser cutter, is inserted into the anterior part of the inferior nasal turbinate of each nostril. The nostrils are clamped shut using a padded nose clip for two minutes. Strips are then removed from the nostril and collected in 1.5ml tubes. They are then stored in strips in a -20°C freezer until elution.

***Venipuncture:***

Venous blood will be obtained by venipuncture for various exploratory endpoints and for cotinine and NNAL levels to detect recent tobacco or e-cigarette use.

***Spirometry and Peak Expiratory Flow (PEF) Measurement:*** Standard methodology conforming to the American Thoracic Society guidelines for measurement of spirometry and peak exploratory flow will be used.

***Allergy Skin Testing:***

Allergy skin testing is performed epicutaneously, examining wheal and flare reactions to histamine, a glycerol control, and various allergens. A Greer® Pick® device that has been immersed in a solution of allergen extract purchased from Greer® Laboratories is used to apply allergen epicutaneously by placing the device at a 45 degree angle to the skin and gently lifting up to create a skin prick. Reagents are obtained from Greer Laboratories and tests are performed as outlined for FDA approved procedures for evaluation of allergy. All testing instruments are single patient use. Each patient will undergo skin prick testing with the following allergen preparations: House Dust Mite (*D. farinae*), House dust mite p (*D. pteronyssinus*), Cockroach, Tree mix, Grass Mix, Weed Mix, Mold Mix 1, Mold Mix 2, Rat, Mouse, Guinea Pig, Rabbit, Cat and Dog. The allergens will be placed on the forearm. After 15 minutes, a research coordinator will compare the wheal size (a raised bump surrounded by red itchy skin) for each allergen to that of the negative and positive control (histamine). A positive skin test is defined by a 3 mm wheal greater than the saline control. For a volunteer to be considered non-allergic, the histamine control must be reactive and all others must be negative.

***Nasal Epithelial Biopsy:***

This is a non-invasive biopsy procedure performed to retrieve a small cluster of cells from each of the nasal cavities. For the nasal biopsy procedure, the subject will be seated comfortably in a straight-backed chair or reclining on an examination table with the head tilted as far back as possible while remaining comfortable. Subjects will be given no medication, sedation, or anesthesia for this procedure. A short, sterile plastic sampling device called a curette will be inserted into one of the nasal cavities and the surface of the nasal cavity will be stroked several times for approximately 5 seconds in order to obtain a small cluster of cells. Due to the potential for the biopsy itself to create a local inflammatory response, we will ensure that visit 2 occurs no sooner than 14 days after visit 1 to allow for dissipation of this inflammatory response before collection of nasal fluid samples. We will sample nasal epithelium from the right nare during visit 1 and from the left nare during visit 2 to ensure we obtain adequate epithelial samples on each occasion.

***Table of Study Procedures***

Procedures to be performed at various time points are listed in the following table and in the accompanying study worksheets.

	Screening day	24 hrs post challenge (phone)	Baseline Visit	Allergen Challenge day	24 hrs post challenge (phone)	Discontinuation visit
Consent	X					
Collect smoking diaries (if applicable)			X	X		
Review history/AE's	X	X		X	X	X
Follow up symptom score		X			X	X
Urine HCG (prior to challenge)	X		X	X		
Vital signs	X		X	X		X
Spirometry/PEF	X			X		X
Physical exam	X			X		X
Total nasal symptom score	X			X		
Peak nasal inspiratory flow rate	X			X		
Allergen challenge	X			X		
Nasal lavage				X		
Nasal epithelial cell collection			X	X		
Epithelial lining fluid collection				X		
Venipuncture	X			X		

### ***Post Challenge Observations: Reporting***

Within 24 hours after allergen challenge, each volunteer will be evaluated using the Follow up Symptom Score described above. If the symptom score is 6 (out of 12), if any single symptom is scored at 3, or if the answers to questions 2, 3, 4, or 5 are “yes”, then subjects will be offered the opportunity to come back to the laboratory for follow-up assessment.

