#### **Post Nasal Allergen Challenge Telephone Follow up (24 hours after Visit 0)**

Subjects will be contacted for phone call follow-up 24 hours after allergen challenge (see phone script included in the study worksheets section)

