#### **Visit 1: Baseline visit (at least 7 days but within 2 months of screening)**

1. Review of medical history including present medications
2. Obtain diaries detailing number of e-cig uses or number of cigarettes smoked per day (e-cig users and cigarette smokers only)
3. Urine pregnancy test for females of child bearing potential.
4. Nasal epithelial cell sampling of the right nare for mRNA to evaluate TLR2, TLR3, TLR4, TLR7, NLRP3, NLRP12, and CD14 expression)
5. Discharge to home.

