***Follow-up Symptom Score (administered by telephone for post-challenge observation):***

1. On a scale of 0 to 3, with 0=no symptoms, 1=mild symptoms, 2=moderate symptoms, and 3=severe symptoms, please rate the severity of each of the following symptoms:

Sneezing (0-3) \_\_\_\_\_  
Congestion (0-3) \_\_\_\_\_  
Nasal Itching(0-3) \_\_\_\_\_  
Rhinorrhea(0-3) \_\_\_\_\_

2. Do you have any health concerns since we saw you on the day of the challenge?
3. Have you needed to see a doctor for any reason since your last visit?
4. Have you needed to use any over the counter medications?
5. Have you had any specific problems with nasal discomfort, cough, wheezing or have you needed any extra allergy or asthma medicines?

If the symptom score is 6 (out of 12), if any single symptom is scored at 3, or if the answers to questions 2, 3, 4, or 5 are “yes”, then subjects will be offered the opportunity to come back to the laboratory for follow-up assessment.

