### ***Definition of an adverse event (AE) and Serious Adverse Event (SAE):***

An adverse event for a given volunteer will be defined as failure of any of the safety criteria outlined in section “e”. Additionally, minor upper respiratory tract infections occurring within 96 hours of the exposure will be considered adverse events. Other, non-specified clinical illnesses, which occur within 96 hours of each challenge, will also be reported as an AE. Any decrease in lung function or increase in symptom score, as outlined in section “e” will be considered an adverse event. Any symptoms that induce a

volunteer to seek medical attention from any provider within 96 hours of challenge will be considered an adverse event.

Adverse events will be graded using Common Terminology Criteria for Adverse Events v3.0, (CTCAE website at <http://ctep.cancer.gov/reporting/ctcnew.html> and <http://safetyprofiler-ctep.nci.nih.gov/CTC/CTC.aspx>). Symptom scores will be graded as outlined elsewhere in this application.

The severity grades of AE's are defined as follows:

Grade 1: Mild AE

Grade 2: Moderate AE

Grade 3: Severe AE

A serious adverse event will be defined as any event that requires hospitalization or results in life threatening illness or injury, permanent (or likely to be permanent) illness or injury, or death if these events occur within 96 hours of challenge (or if the clinical scenario leading up to hospitalization, illness, injury or death begins within 96 hours of a challenge).

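### After the Visit 0 challenge the only scheduled enquiry in the 96-hour event window is at 24 hours, so later events are likely to be recognised late and dated from memory

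*Combined protocol and SAP*

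**What the plan says.** The section defining adverse and serious adverse events ties several kinds of event to a 96-hour window:

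- Respiratory infections: "minor upper respiratory tract infections occurring within 96 hours of the exposure will be considered adverse events".
- Other illnesses: "Other, non-specified clinical illnesses, which occur within 96 hours of each challenge, will also be reported as an AE".
- Care-seeking, where symptoms lead a "volunteer to seek medical attention from any provider within 96 hours of challenge will be considered an adverse event".
- SAEs: hospitalisation, life-threatening or lasting harm, "or death if these events occur within 96 hours of challenge". This extends to cases where the course leading to the outcome starts inside the window.

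AEs defined as failure of the individual safety criteria (under Safety measures) carry no 96-hour limit.

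Visit 0 is itself an allergen challenge, graded up to 1,000 AU. The follow-up scheduled after it is one call: "Subjects will be contacted for phone call follow-up 24 hours after allergen challenge". The reporting section puts it slightly differently: "Within 24 hours after allergen challenge, each volunteer will be evaluated using the Follow up Symptom Score described above". The telephone script is suited to the purpose, since it asks "Have you needed to see a doctor for any reason since your last visit".

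The next contact is "Visit 1: Baseline visit (at least 7 days but within 2 months of screening"). Its first item is a review of history and current medication. In the Table of Study Procedures, the row for history and AE review is blank in the Baseline column. It is marked for screening, both calls, the Visit 2 challenge day and the discontinuation visit. That last visit falls 5 to 10 days after the Visit 2 challenge and includes an examination and spirometry.

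**The concern.** The window over which events count and the schedule for asking about them do not match after the first challenge. The one planned call comes when a quarter of the window has passed. A subject who develops a cold on day 2, or sees an outside clinician on day 3, has a countable event. Staff would learn of it only if the subject rings the on-call physician or mentions it at Visit 1 or later. A minor illness gives little reason to ring. Whether it began inside 96 hours must then be settled from memory.

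Two items under Safety measures can also arise after discharge. One is a need for oral corticosteroids, which counts towards the 9 individual failures that suspend the study. The other is any SAE, which suspends it outright. The 24-hour SAE report runs from recognition, so late recognition breaches no deadline, but it does delay the report. Other subjects could be challenged before it is known that a suspension criterion has been met.

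**Working it through.** The plan states no figure on this point, so the check is timeline arithmetic.

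**Inputs**
- Event window: 96 h after each challenge (AE and SAE definitions).
- Scheduled call: 24 h (telephone follow-up after Visit 0). If it is made earlier, as the reporting section allows, the stretch without enquiry is longer.
- Visit 1: day 7 to 2 months after screening. I take screening as Visit 0 and 2 months as 60 days.
- Discontinuation visit: day 5 to day 10 after the Visit 2 challenge.
- Proposed call: 96 to 120 h after the Visit 0 challenge.

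**Part of the window after the only scheduled call:** 96 − 24 = 72 h, and 72/96 = 75%.

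**Wait from onset to the next scheduled contact.** Wait = time of contact − time of onset, for onset between 24 and 96 h.

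| Challenge and next contact | Shortest wait (onset at 96 h) | Longest wait (onset at 24 h) |
|---|---|---|
| Visit 2, discontinuation visit on day 5 to 10 | 120 − 96 = 24 h (1 day) | 240 − 24 = 216 h (9 days) |
| Visit 0, Visit 1 on day 7 | 168 − 96 = 72 h (3 days) | 168 − 24 = 144 h (6 days) |
| Visit 0, Visit 1 on day 60 | 60 − 4 = 56 days | 60 − 1 = 59 days |
| Visit 0, with the added call | 96 − 96 = 0 h | 120 − 24 = 96 h (4 days) |

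As planned, the wait after Visit 0 runs from 3 to 59 days, against 1 to 9 days after Visit 2. If Visit 1 is on day 7, its 3 to 6 days lie within the range the plan already accepts after Visit 2. The shortfall appears as Visit 1 moves later, and the documents do not say when it will usually be held.

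**Number of calls.** At least 45, the recruitment goal. If 10% to 50% fail screening (my assumption; no rate is given), the number is 45/0.9 = 50 to 45/0.5 = 90.

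**The case against.** The case against giving this much weight is substantial.

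*Visit 1 does ask.* The Visit 1 and Visit 2 lists open with the same history review, and the table marks AE review at Visit 2. The blank Baseline cell therefore looks like a missed tick. The table departs from the visit lists elsewhere too, for example by marking vital signs at Baseline and venipuncture at screening. The study worksheets, which may settle the matter, are not in the documents. This stands. A reader might infer that no AE enquiry takes place until Visit 2, at the earliest day 7 + 14 = 21, which is 17 to 20 days after onset. That figure treats the blank cell as decisive, and the visit lists do not support it.

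*Eligibility checks overlap.* Challenge is barred within 4 weeks of a viral respiratory infection or one needing antibiotics, and within 12 months of emergency asthma treatment or systemic steroids for an exacerbation. Re-applied before the Visit 2 challenge, these rules would bring out steroid-treated exacerbations, and infections when Visit 2 is early. This stands in part. The re-check is implied rather than scheduled. Counted from onset, the 4-week look-back no longer reaches the window once Visit 2 is later than day 28 + 4 = 32.

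*Screen failures may be covered.* The Study discontinuation visit text asks each subject to return within 10 days of the last challenge dose, which for a screen failure is at Visit 0. That reading is possible, but the visit list and the table place the visit after Visit 2. For subjects who continue, the final dose is at Visit 2, so that text does not close their Visit 0 window.

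*Other safety nets exist.* A physician is on call at all hours, and a symptomatic 24-hour call leads to an offer of a return visit. Both help. The first relies on the subject, and the second cannot act on an event that has not yet begun.

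*Risk looks low.* Monitoring and risk minimization reports over 70 earlier challenges with no anaphylaxis or acute bronchospasm. This is reassuring, although those studies did not measure lung function regularly afterwards. They also describe a cumulative 1,100 AU, against the 1,600 AU maximum here.

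**Conclusion.** The mismatch is real but minor. It concerns intercurrent illnesses, care-seeking symptoms and SAEs that start 24 to 96 hours after the Visit 0 challenge. Such events are likely to be recognised about 3 to 59 days after onset and dated by recall, against 1 to 9 days after Visit 2.

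A reader might go further and conclude that these events would be missed. The documents do not support that. Visit 1 includes a history review, and a hospitalisation or life-threatening illness is unlikely to go unmentioned there. Nor is any stated reporting deadline breached.

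The consequences are less certain dating of mostly minor AEs and possible delay in SAE reporting and in the suspension rules. The primary endpoint is unaffected. The size given is a waiting time, not a count of events, because the documents give no rate of late events. It rests on taking 2 months as 60 days, on Visit 1 being the next contact, and on the subject not using the on-call line.

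**What to change.** Add one call, using the existing telephone script, at 96 to 120 hours after the Visit 0 challenge for everyone challenged. Include screen failures unless they attend a discontinuation visit. Mark the history and AE review row at the Baseline visit so that the table agrees with the Visit 1 list. No extra call is needed after Visit 2, because the visit at 5 to 10 days already closes that window.

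With the call, the wait from onset falls to 0 to 4 days. The gain is prompt, datable capture, not examination during the reaction. The cost is one short call per subject challenged at Visit 0 (at least 45) and one mark in the table, with no new visit, sample or procedure.

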### ***Study discontinuation visit:***

Within 10 days of the final challenge dose, each subject will be asked to return for a study discontinuation visit. At that time temperature, pulse, systolic and diastolic BP, respiratory rate, FVC and FEV1, and symptoms scores will be assessed and, if abnormal, medical evaluation as directed by the study physician will be undertaken.

### ***Definition of an adverse event (AE) and Serious Adverse Event (SAE):***

An adverse event for a given volunteer will be defined as failure of any of the safety criteria outlined in section “e”. Additionally, minor upper respiratory tract infections occurring within 96 hours of the exposure will be considered adverse events. Other, non-specified clinical illnesses, which occur within 96 hours of each challenge, will also be reported as an AE. Any decrease in lung function or increase in symptom score, as outlined in section “e” will be considered an adverse event. Any symptoms that induce a

volunteer to seek medical attention from any provider within 96 hours of challenge will be considered an adverse event.

Adverse events will be graded using Common Terminology Criteria for Adverse Events v3.0, (CTCAE website at <http://ctep.cancer.gov/reporting/ctcnew.html> and <http://safetyprofiler-ctep.nci.nih.gov/CTC/CTC.aspx>). Symptom scores will be graded as outlined elsewhere in this application.

The severity grades of AE's are defined as follows:

Grade 1: Mild AE

Grade 2: Moderate AE

Grade 3: Severe AE

A serious adverse event will be defined as any event that requires hospitalization or results in life threatening illness or injury, permanent (or likely to be permanent) illness or injury, or death if these events occur within 96 hours of challenge (or if the clinical scenario leading up to hospitalization, illness, injury or death begins within 96 hours of a challenge).

*Measures to minimize risk:* Only people with allergic rhinitis and/or mild asthma, as characterized the NHLBI guidelines for the diagnosis and management of asthma, will be recruited for this project. Please note that our exclusion criteria for subjects include symptom or medication use criteria that would result in classification of an asthmatic as moderate or severe. Further, subjects will be deferred for challenge until 4 weeks after complete resolution of each of the following acute illnesses: viral respiratory tract infection, pneumonia or bronchitis requiring antibiotic therapy (must be off antibiotics and well for 2 weeks after the last dose of antibiotics, 4 weeks in the case of azithromycin due to its prolonged half-life), or acute illness resulting in fever. Also, unspecified illnesses, which in the judgment of the investigator increase the risks associated with allergen inhalation challenge, will be a basis for exclusion. As outlined above in section *e*, all subjects will need to fulfill objective lung function and symptom criteria prior to initiating a specific challenge study.

A physician familiar with the protocol will be available for all challenge procedures. Emergency treatment with topical and intramuscular epinephrine, albuterol, oxygen, antihistamines and oral corticosteroids will be available to those patients who require such therapy. The human exposure laboratory is also equipped with an emergency “crash cart” with standard emergency medications, IV fluids and a defibrillator in the unlikely event of a medical emergency for any challenge study.

All subjects will be will be monitored as outlined in previous sections. A follow-up call will be made 24 hours after challenge to ensure that subjects are well, and all subjects will be provided with a contact telephone number for access to a study physician who is on call 24 hours/day. Subject may be withdrawn from the study at any point if the physician determines it is in the best interest of the subject.

#### *Reporting of AEs and SAEs*

All SAEs will be reported to the CBER of the FDA as well as to the UNC Biomedical IRB within 24 hours of recognition of the event. Adverse events will be reported to both the FDA and UNC IRB on no less than a quarterly basis, or when the protocol is completed. If criteria for suspension of the protocol are met, then the FDA and UNC IRB will be notified within 24 hours.

All subjects with a non-fatal SAE will be evaluated medically by a study physician, in concert with their own physician as appropriate. Likewise all subjects with an adverse event will be examined and evaluated by a study physician. All assessments will include the same lung function and vital sign assessments outlined for challenge observation. Other assessments will be undertaken as needed. Any unspecified event, which in the judgment of the PI of the study, constitutes an unusual, unexpected or prolonged event (greater than 96 hours) will be reported to both the FDA and the UNC IRB.

Curriculum Vitae for investigators are appended to this application.

### ***6.2. Informed Consent***

Investigators and study staff will explain all study procedures and the benefits and risks of the study to potential participants as part of obtaining informed consent. Subjects may withdraw their consent at any time during the study. If they withdraw from the study it will not impact the care they receive at UNC or its affiliated hospitals and clinics.

